We do not anticipate adverse events associated with these non-interventional qualitative interviews, however it is possible that discussing their care could trigger upset for patients. In the event of psychological harm experienced during the interview, immediate verbal support will be offered to the participant and the interview ended if necessary. Such adverse events will be recorded and discussed with the study team. With participant consent, arrangements will be made for local support to be offered at their hospital by way of contact with the hospital clinical lead and/or their general practitioner. The study sponsor will be notified within 24 hours as per local NHS R&D procedures. An electronic copy of any adverse event form will be stored in the project specific site file.

It is possible that during the interview a patient could report symptoms in keeping with a potential ongoing complication that requires medical attention. In such instances, the interview would be terminated and a minimum set of relevant questions asked in order to be able to give advice to the patient about how to seek medical attention. Advice would involve one of the following, depending on the potential severity of the underlying problem; arranging a GP review, patient-arranged emergency department attendance, or the interviewer calling emergency services for emergency paramedic assessment and transport to hospital.

It is also possible that descriptions of medical malpractice could be described by a participant during their interview. In such an instance, relevant detail would be obtained and the matter discussed within the study team to develop an appropriate strategy. As a minimum this would involve feeding concerns back to the hospital's urology clinical lead in order for the matter to be addressed. If felt to be necessary, escalation of concerns to the GIRFT urology programme, NHS England for the General Medical Council would be considered, depending on the nature of the issue.

Benefits to participants:

There are no financial incentives for participation. Participants will hopefully appreciate the opportunity to discuss their observations about their experiences of a real-world health service. There is an opportunity for them to provide detailed insights that could drive wide service improvement. On this basis, it is hoped that they will find the process an empowering one, in particular knowing that their input will contribute to a larger research project which could inform future practice through a quality improvement programme taking place on a national scale (the GIRFT programme).

Risks to researchers:

There are no anticipated risks to the researchers. Any interviews will be conducted virtually or in public areas.

Participant feedback

An opportunity for anonymous participant feedback will be offered following the interview using Survey Monkey. Feedback will be stored in the study file on the Royal Devon and Exeter Hospital encrypted server.

Dissemination/implementation of research

Results will be written up and submitted for publication in a peer-reviewed journal. Abstracts will be submitted to national and international conferences. Results will be presented to clinical colleagues at regular in-house meetings. Results will be shared as part

of future GIRFT reports and the findings might influence future GIRFT recommendations. Written information in the form of a summary report outlining the key findings of the study will be sent to all participants and any stakeholders including PPIE representatives who were involved in the study design and implementation. This will be in electronic format with an option of a hard copy on request.

Potential impact and benefit of the proposed research:

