Aim	To understand patient experiences following day-case transurethral resection of bladder tumour (TURBT), transurethral resection of prostate (TURP), and transurethral enucleation of prostate (TUEP).
Main Criteria for Inclusion	
Inclusion Criteria:
 
 ● Adults aged >18 who have recently undergone day-case TURBT or TURP or TUEP ● Able and willing to provide informed consent 
Exclusion Criteria:
 
 ● Patients who had surgery that was not performed as a day-case
Study Duration	18 Months
Study Period	April 2023 – October 2024
Study Summary	
A qualitative research study interviewing patients treated in hospitals across England. We will interview patients who have recently undergone one of the following operations as a day-case; transurethral bladder tumour resection (TURBT), transurethral resection of prostate (TURP) or transurethral enucleation of the prostate (TUEP). We are interested to find out about the experience for patients who go home on the day of surgery after they have had one of these operations. We hope that the findings will tell us about how to improve the experience for patients in future.
 
Patients undergoing day-case surgery at a range of different hospitals from across England with varying day-case rates will be interviewed. Hospitals in large city and more rural areas will be included. Interviews are anticipated to take place over a six month period between December 2023 and May 2024. The study will end when “saturation” is achieved, whereby no new themes are identified through interviews. Saturation

	will be sought for each individual operation of interest. Analysis and write up will take place from May 2024 – October 2024.
--	---

Table of Contents

Amendment History/Changes from previous version	7
Scientific Summary	8
Plain English Summary	9
Research Question	9
Aims and Objectives	10
Aim:	10
Objectives:.....	11
Methods	11
Study Population	11
Inclusion criteria	11
Exclusion Criteria	12
Participant Identification:.....	12
Screening and identification	12
Recruitment.....	12
Informed consent.....	13
Participant withdrawal:.....	14
Schedule of events	16
Primary outcome measure:	16
Study management	17
Budget Summary and costings	18
Project development and user involvement	18
Data Management	20
Data monitoring:.....	20
Data Confidentiality:	20

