We want to know what it is like for patients who go home on the day of surgery. We hope that this will tell us how to improve the process for patients in future.

We will perform the study through hospitals that do a lot of day-case surgery for bladder tumours or prostates. Before or after surgery the doctor will ask their patient if they would be happy to be interviewed. This would take place in the future after they have fully recovered. Patients will be given an leaflet explaining the study. This will have an email address and phone number to contact if they would like to take part.

Willing patients will be interviewed one-to-one on the internet or phone. Each patient will be asked about their experience of having day-case surgery. The interviews will be recorded. After, the research team will listen to them to find common patient experiences. They will look for ways that future patient's experiences could be made better.

Research Question

What is the patient experience of day-case TURBT, TURP and TUEP?

Rationale and background

Resource constraints and evolving patient demographics mean that the waiting lists for elective surgery in the NHS are greater than ever. Nationally, the median average percentage of patients receiving transurethral resection of bladder tumour (TURBT) treatment within 62 days of referral is only 13.1% (1). For patients requiring surgical treatment for acute urinary retention, the median average national hospital wait time exceeds five months (1).

Solutions are required to improve timely patient access to surgery. The approach will need to be multi-factorial, and increasing day-case rates by configuring safe and effective pathways is one proposed method (2). Performing common endourology operations as a day-case when possible, could take pressure off inpatient resources and allow these inpatient beds to be used for other purposes (3). It also means that these endourology operations could proceed without a reliance on inpatient bed availability, and this would open opportunities to perform surgery in peripheral day-case units without inpatient beds (4). Furthermore, by utilising less resource intensive day-case pathways there would be cost savings, and potentially reduced associated greenhouse gas emissions (5). There is additionally reason to suppose that patients might have a superior experience by recovering at home instead of as a hospital inpatient, although this has not yet been demonstrated in academic literature.

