We hypothesise that the patient experience of day-case TURBT, TURP and TUEP is acceptable when delivered as part of a well-designed treatment pathway.

Choice of study design:

A semi-structured qualitative interview design has been adopted in order to identify key themes.

We see it as important to interview a range of patients having undergone TURBT, TURP or TUEP, at different hospitals in different parts of England. This is so we can gain a broad range of perspectives about different care pathways that have been developed, and to gain a broad representation of the patient experience. We will conduct interviews with patients who have had surgery at hospitals with different day-case rates because it is possible that factors relevant in one hospital that performs a certain volume of day-case endourology surgery might not be the same in other hospitals.

Methods

Study Population

Patients who have recently undergone day-case transurethral resection of bladder tumour (TURBT), transurethral resection of prostate (TURP), or transurethral enucleation of the prostate (TUEP) at an NHS hospital in England.

Inclusion criteria

- Adults aged ≥ 18
- Experienced day-case TURBT, TURP or TUEP within the past 6 weeks
- Willing and able to provide informed consent
- English speaking

Exclusion Criteria

- Experienced surgery that was not performed as a day-case

Potential participants will not be excluded on unfair grounds, however participants will be selected from a pool of willing individuals such that a representative cross section of different individuals are interviewed based on demographics and location.

Participant Identification:

Screening and identification:

Study sites of interest will be identified by analysing Hospital Episode Statistics (HES) data using the Model Hospital information dashboard. A representative selection of hospitals performing high, intermediate and low rates of day-case surgery for the operations of interest will be selected for potential recruitment. Representation of urban and rural areas, and patient population demographics will be considered to gain a representative cross section of English hospitals.

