Clinicians who perform any of the operations of interest as a day-case will be contacted and consented to assist with participant identification. This will involve discussing the study with patients on the day of their operation, after standard preoperative consenting has taken place and before any anaesthetic or preoperative psychoactive medications are administered. Expression of interest will be noted and a study information leaflet provided for patients who are interested in participation.

The individuals gaining the expressions of interest from patients will be considered as local collaborators rather than investigators, and the recruitment sites as participant identification centres (PICs) rather than formal study sites.

Potential participant's details will be sent from their treating clinician/local collaborator to the sponsor site Principle Investigator (PI) via secure encrypted NHS email. The following details will be included; operation type and date, contact details, age, sex, ethnicity, and whether the patient has a carer. Potential participant contact details will be stored at the sponsor site on a database on a secure server and screened in order to gain interviews with a diverse patient population.

Potential participants will then be screened based on their demographics, operation type, and hospital, and contacted by telephone to discuss participation in further detail.

Recruitment:

The research team will then be responsible for the recruitment process. This will include a telephone call from a member of the research team to identified potential participants, and

providing an electronic study-specific participant information sheet (PIS). A physical PIS will be offered by post if preferable. Potential participants will be provided with the opportunity to discuss the project in detail with a member of the research team. These discussions will include the nature and purpose of the study, participant involvement and potential risks. All potential participants will be given the time they deem necessary to make the decision to participate. The anticipated time commitment associated with undertaking the interview will be explained. Data on numbers of participants expressing interest to take part, invited to take part, and those actually taking part, will all be recorded.

Informed consent:

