The participant information sheet contains sufficient detail in order for individuals to be able to make an informed decision about participation. Participants will be offered opportunities to ask any further questions that they might have either by email or over the telephone, with the sponsor site PI. If necessary, a physical PIS copy will be posted to potential participants if they are unable to access email.

Willing participants will be routinely contacted by telephone on a date ahead of the interview to answer any questions, confirm their willingness to participate, and arrange a suitable date and time for interview.

Since the interviews are largely planned to take place remotely either using video conferencing (MS teams) or over the telephone, verbal consent will be obtained and recorded prior to the interview. This will be on the day of the interview, after permission to record has been granted and before the interview questions commence.

On the day of the interview, before commencing the interview, the consent form will be read out to the participant. Each point will be read out in turn and ticked when the participant agrees to them. Opportunities to ask further questions will be offered after each point. The participant will be asked to provide verbal consent and this will be recorded on audio. The audio files of participation consent will be stored on a password protected secure server at the sponsor site, separate from the main body of their interview but linked via a pseudonymised participant identification number. On providing their verbal consent, the interviewer will also sign the consent form and send a copy via e-mail to the interviewee.

Recordings of consent will be saved and stored as separate files on a password protected encrypted server at the sponsor site (Royal Devon University Healthcare NHS Foundation Trust). A delegated member of the research team will maintain a record of all documented consent.

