Data will be analysed on password protected NHS computers at the sponsor site by the principle investigator and a further research associate. A small subset of pseudonymised transcripts will be emailed to the PPIE representative's university of Exeter email account for analysis on a University of Exeter computer.

Data Storage and Archiving:

All electronic documentation of consent, electronic data collection forms, and audio/video files will be stored on an encrypted, password protected server at the Royal Devon and Exeter Hospital, with regular file backup. The server is stored in a dedicated secure facility. Data transfer to this server will be via password protected encrypted NHS email, or using a password protected encrypted USB storage device. Any paper copies of data will be stored in lockable filing cabinets within the Royal Devon University Healthcare NHS Foundation Trust (RDUH) Urology Department offices. Archiving will be undertaken as per current standard RDUH R&D protocols and procedures. Study data will be stored at the sponsor site for 5 years, in keeping with sponsor site research and development standard operating procedures.

Ethical considerations

We have identified the potential ethical considerations and addressed them below:

Altered or impaired mental state: Only adults with capacity to consent to participation will be approached for potential involvement. Expressions of interest will be obtained in a comfortable environment before any anaesthetic is delivered. Formal consent will only be obtained once the patient has fully recovered from anaesthetic, approximately one week after surgery. We have discussed this matter with our PPIE group and it was felt to be acceptable to gain expressions of interest from patients on the day before their operation, after they had been consented for surgery.

Concerns about quality of medical care: Patients will be reassured by the team providing their care that no alterations to their usual standard of care will take place. The PIS will help to explain this.

Time burden: Participants will be reassured that their involvement in the study is voluntary and that they are able to withdraw at any time. A convenient interview time will be arranged for each study participant.

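### Do the differing statements on interview timing, and the unanchored six-week limit, leave the interview window undefined?

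*Protocol*

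**What the plan says.** The Protocol touches on interview timing in several places.

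- **Ethical considerations (altered or impaired mental state):** "Formal consent will only be obtained once the patient has fully recovered from anaesthetic, approximately one week after surgery".
- **Informed consent:** verbal consent is taken immediately before the questions: "This will be on the day of the interview, after permission to record has been granted". An earlier call arranges it: "Willing participants will be routinely contacted by telephone on a date ahead of the interview".
- **Plain English Summary**, on the interview: "This would take place in the future after they have fully recovered".
- **Inclusion criteria:** "Experienced day-case TURBT, TURP or TUEP within the past 6 weeks". The synopsis has no figure, only adults "who have recently undergone day-case TURBT or TURP or TUEP".
- **Screening and identification**, on the first approach: "This will involve discussing the study with patients on the day of their operation, after standard preoperative consenting has taken place".
- **Exclusion Criteria:** "participants will be selected from a pool of willing individuals".
- **Interviews, Timing:** a date that suits the interviewee, within the study timeline.
- **Schedule of events:** the inclusion/exclusion check is time point 4, consent is 5 and interview is 6. None of the three is dated relative to surgery.

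**The concern.** A reader looking for one surgery-to-interview window does not find it stated. One section points to about a week, another to full recovery with no number, and a third to any date that suits. The only upper limit tied to surgery has no reference day. It cannot be applied at the first approach, because the operation has not yet happened. Selection from the pool, the recruitment call, time to decide and the booking call can all separate the eligibility check from the interview.

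The primary outcome is what patients say about their experience. An interview at one week can cover one week at home, while one at six weeks covers more recovery and leans more on recall. If the lay summary's condition were enforced together with the six-week limit, patients with a slow or complicated recovery could be left out. Days since surgery are also absent from the list of descriptive data, so readers might not see how far the interval varied.

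**Working it through.** No power, error rate or sample-size figure is involved. The check is a comparison of passages plus simple arithmetic on the stated intervals.

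**Floor.** The ethics section puts consent at about 1 week, or 7 days. The Informed consent section puts consent on the interview day. Together they mean that the interview falls at about day 7 or later. The ethics sentence concerns capacity after anaesthetic, so it sets an earliest time and does not fix an appointment date.

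**Ceiling, first reading.** If the six weeks are counted on the consent and interview day, the latest interview is at 6 × 7 = 42 days. The window is 42 − 7 = 35 days (5 weeks), and the ratio of longest to shortest interval is 42 / 7 = 6.

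**Ceiling, second reading.** If the six weeks are counted at time point 4 of the schedule, the eligibility check falls by day 42 but the interview can come later. It is then limited only by the study calendar. The synopsis expects interviews from December 2023 to May 2024: 31 + 31 + 29 + 31 + 30 + 31 = 183 days, about 26 weeks. That is a limit on paper, and nothing in the Protocol suggests that interviews would be left so long.

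**Do the figures conflict?** One week lies inside six weeks, so they do not. The Timing paragraph lets the participant choose a date, but it does not suspend the eligibility criteria. On the first reading, floor, ceiling and convenience are compatible.

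**Is full recovery a condition?** It appears in neither eligibility list (synopsis or Methods). The section on adverse events provides for interviewees who report symptoms of an ongoing complication, which would make little sense if incomplete recovery barred an interview. The lay sentence is best read as a loose version of recovery from anaesthetic.

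**Where would the interval matter?** Most questions in Appendix 1 deal with the day of surgery: the information given, the feeling about same-day discharge, going home and the journey. The question on managing at home is the one most exposed to time since surgery.

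**Can the interval be recovered?** Yes. The operation date is sent with the referral details, and the consent record is made on the interview day. The difference between the two dates gives days from surgery to interview without new data collection.

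**The case for a change.** The strongest case for a change is that an eligibility criterion should say when it is assessed, and this is protocol content that cannot be left to an unseen analysis plan. Two members of the team could apply the six weeks at different steps and both comply. The Scientific Summary names the lived experience after discharge as what is poorly understood, so time at home bears on the question asked. If the interval differed by operation or hospital, a difference in themes could partly reflect time since surgery. Clarifying the wording would also cost little.

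Part of this stands. The reference day is not stated, the schedule supports a reading under which 42 days does not cap the interview, and the lay summary is worded differently from the ethics section.

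The consequence does not stand. Nothing in the Protocol shows that an interview would be lost or a theme altered. The design deliberately seeks a broad range of perspectives, and some spread in time since surgery is compatible with that. The loss of slow recoverers requires staff to enforce a condition found in neither eligibility list. Reporting the interval is a presentational choice that remains open, since both dates are held. Choosing the window is for the investigators, who took advice from the patient and public group on when to schedule interviews.

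**Conclusion.** The concern identifies loose drafting, not a fault in the design. The statements give a floor of about 7 days and, if the limit is counted on the interview day, a ceiling of 42 days: a 35-day window. If it is counted at the eligibility check, the interview is bounded only by the study calendar, so the 35-day figure holds on one of two readings. On either reading no lost interview and no shift in themes has been shown.

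This rests on three assumptions: that consent and interview share a day, as the Informed consent section says; that the lay summary's phrase is not used as an eligibility rule; and that the operation date sent at referral is retained. On that footing the study team can settle the reference day in practice, and the analysts can describe time since surgery if they wish. Following the plan as written would still give sound results for a thematic study of this kind, so no change is called for.
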